## 7.3 Analysis of Secondary Outcomes

### 7.3.1 Duration of Symptoms, Missed Daycare and Missed Work

Duration of diarrhea, duration of vomiting (components of the MVS), days of missed daycare, and hours of missed work will be analyzed in a similar manner. Groups will be compared using the Van Elteren test, stratified by center and duration of symptoms (pre-enrollment). Analysis of duration of vomiting, missed daycare, and days of missed work will be restricted to the populations in which the measures are applicable. Additional analyses involving these outcomes will include linear regression models that adjust for possible effects of baseline characteristics.

### 7.3.2 Return Visits

Return visits will be assessed as to whether or not they are related to vomiting, diarrhea, dehydration, fever, or fluid refusal. If any such visit occurs within 2 weeks of the index visit, it will be counted for this outcome. The outcome will be compared between treatment groups using the Mantel-Haenszel test, stratified by clinical center and duration of symptoms.

## 7.4 Safety Outcomes

### 7.4.1 Side-Effects

The occurrence of any side-effect (listed previously) will be analyzed as a dichotomous variable for two time windows: the initial disease window (through day 14, or until resolution of symptoms) and through day 35 (which includes the initial window). The first of these two windows will not count diarrhea, vomiting, fever, or diaper rash as these will likely be experienced by a vast majority of subjects and are part (with the exception of diaper rash) of the primary and secondary outcomes. The latter window will only count diarrhea, vomiting, fever, or diaper rash that occur after the initial disease window.

The outcome will be compared between treatment groups using a Mantel-Haenszel test, stratified by center and duration of symptoms prior to randomization.

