## 5 Data Analysis

The hypotheses of this study are:

1. In children with acute gastroenteritis, probiotic administration in the emergency department will be associated with a clinically-important decrease in the proportion of children suffering from moderate-severe disease, defined by a validated Modified Vesikari Score  $\geq 9$ , compared to placebo.
2. In children with acute gastroenteritis, probiotic administration will not be associated with serious adverse events, and will have a similar rate of side effects (e.g. bloating, fever) as compared to placebo-treated children.

All analyses will be undertaken by the intention-to-treat (ITT) principle, except for adverse events, which will use the as-treated principle (compare the subjects based on the treatment regimen that they received). Patients who drop out or inadvertently crossover will be followed and included in the ITT analysis. All statistical tests of hypotheses will be two-sided. Baseline characteristics will be analyzed to determine if there is a need to adjust for differences between groups in exploratory analyses. Sensitivity analyses will be performed to assess the possibility and consequences of non-random loss to follow-up. The proportions of children experiencing an unscheduled healthcare visit or any potential adverse effect, as reported by the caregivers, will be compared between groups using the Mantel-Haenszel test, stratified by site. The analysis will evaluate the presence/absence of pre-specified side effects, as an aggregate outcome variable. A per-protocol analysis will be conducted to provide additional insight as non-compliance may result in an underestimation of the benefits of probiotics in the ITT analysis.

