### 8.3.2 Time Period for Adverse Events

For purposes of this study, adverse events occur following randomization through 30 days after the last study drug dose will be recorded. Serious adverse events, unexpected medically attended events, and new onset chronic illnesses will be recorded from randomization through twelve months after the last study dose. Specifically, events that occur following parental permission to participate in the study, but prior to actual randomization, are *not* adverse events. These should be recorded as baseline conditions.

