### 8.3.3 Data Collection Procedures for Adverse Events

After patient randomization, all adverse events (including serious adverse events), whether anticipated or unanticipated, will be recorded according to the date of first occurrence, severity, and their duration, as well as any treatment prescribed. Any medical condition present at the time of randomization, recorded in the patient's baseline history at study entry, which remains unchanged or improves, will not be recorded as an adverse event at subsequent evaluations. However, worsening of a medical condition that was present at the time of randomization will be considered a new adverse event and reported.

Abnormal laboratory values that are clinically significant will be recorded as adverse events and the site investigator will assess the severity and relationship to the study. Laboratory values that are abnormal at the time of randomization and that do not worsen

will not be recorded as adverse events.

Adverse events will be coded using the MedDRA coding vocabulary. Coding will be done centrally at the Data Coordinating Center because this requires specific training.

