### 2.2.2 Safety Outcomes

Safety outcomes are:

1. The occurrence of invasive disease (including meningitis and bacteremia) from *Lactobacillus rhamnosus*.
2. Occurrence of side effects: bloating, gas, intestinal rumbling, diarrhea, blood in stool, abdominal pain, abdominal cramps, nausea, vomiting, loss of appetite, heartburn, constipation, skin rash, diaper rash, fever, nasal congestion, runny nose, sore throat, cough, headache, muscle aches, chills, weakness.

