### 7.4.2 Adverse Events

Adverse events (AEs) will be recorded from the time of randomization through 35 days. Symptoms/side-effects described previously will generally not be counted as AEs, as they will be reported separately. Serious adverse events (SAEs), unexpected medically attended events, and new chronic illnesses will be reported from randomization through one year after last study dose. Adverse events will be coded using the Medical Dictionary for Regulatory Activities (MedDRA), version 14.0.

**All Adverse Events** Summaries of incidence rates (frequencies and percentages), intensity, and relationship to study of individual AEs by System Organ Class and Preferred Term (MedDRA) will be prepared. All AEs beginning after randomization but before discharge will be included. Basic summaries by assigned groups will be prepared. The DSMB may request to see more detailed tables. The occurrence of any adverse event will be considered as a dichotomous outcome and will be compared between groups using a Mantel-Haenszel test, stratified by clinical center and duration of symptoms.

**Serious Adverse Events/Deaths** SAEs/Deaths will be reported separately in a similar fashion to the more general AE reports. In addition, narratives will be available for each event.

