## Lactobacillus Rhamnosus GG vs. Placebo for Pediatric Acute Gastroenteritis

### Summary of SAP changes (from version 1.1- January 2015- to V1.2 April 2017)

1. Section 7.2: The definitions of duration of diarrhea and vomiting were changed to incorporate additional details about handling potentially erroneous dates and times. (Pages 13 and 14)
2. Section 7.2.1: Detail was added on the approach for combining results from nonparametric tests across imputed datasets. (Page 15)
3. Section 7.2: A sensitivity analysis was added. This will look at the primary results after excluding subjects with daily surveys that were completed more than 14 days after the corresponding survey day. (page 16)
4. Section 7.4: Diaper rash was added as one of the symptoms not counted in the initial “side effects” window due to an expected high prevalence at baseline and early follow-up. (Page17)
5. Section 7.6: Detail was given on the analysis of subgroup effects related to count outcomes (negative binomial regression). (page 18)

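### SAP 7.4.1 sets no new-onset condition for the any-side-effect comparison, so symptoms carried over from the presenting gastroenteritis can dilute a true difference between arms

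*Combined protocol and SAP*

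**What the plan says.** SAP v1.2 section 2.2.2 lists 23 symptoms, beginning: "Occurrence of side effects: bloating, gas, intestinal rumbling, diarrhea, blood in stool, abdominal pain, abdominal cramps, nausea, vomiting, loss of appetite, heartburn". Section 7.4.1 turns them into one yes/no outcome: "The occurrence of any side-effect (listed previously) will be analyzed as a dichotomous variable for two time windows". The windows run through day 14 (or symptom resolution) and through day 35, and the second includes the first. On exclusions, 7.4.1 states: "The first of these two windows will not count diarrhea, vomiting, fever, or diaper rash". Those four terms count only after the initial window. The SAP change log, item 4, says diaper rash was added to them "due to an expected high prevalence at baseline and early follow-up".

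Protocol V3.0 section 5 describes the outcome in the same way: "The analysis will evaluate the presence/absence of pre-specified side effects, as an aggregate outcome variable".

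The baseline rules belong to adverse events. On events after parental permission but before randomization, protocol 8.3.2 says: "These should be recorded as baseline conditions". Protocol 8.3.3 adds that a medical condition recorded at baseline "which remains unchanged or improves, will not be recorded as an adverse event at subsequent evaluations", while worsening is a new adverse event. SAP 7.4.2 then separates the two categories: "Symptoms/side-effects described previously will generally not be counted as AEs, as they will be reported separately".

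**The concern.** Every child enters with acute gastroenteritis. Nausea, loss of appetite, abdominal pain or cramps, gas and bloating can be present before the first dose and still be reported at the first follow-up contact. Protocol 8.3.1 itself says that bloating and abdominal pain are hard to separate from the illness. The change log shows that baseline prevalence was recognised as a counting problem and dealt with for diaper rash. The remaining 19 terms have no stated baseline condition.

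Because the outcome is any one of 19 symptoms, a single persisting symptom makes a child a yes in either arm, whatever the study drug does. The second primary objective (SAP 2.1.1) is that side-effect rates are similar, and the SAP gives no margin for similarity. A comparison that has lost sensitivity therefore tends to produce the non-significant result that would be read as support for that objective.

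**Working it through.** **1. Scope.** The list has 23 terms. Removing diarrhea, vomiting, fever and diaper rash from the initial window leaves 23 − 4 = 19. Two of these should rarely be present at entry. Blood in stool is one, because hematochezia in the preceding 48 hours is an exclusion. Constipation is the other, because entry requires at least three watery stools in 24 hours.

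**2. Check of the method on the plan's own figure.** The documents give no power or expected rate for side effects, so the formula was checked on the primary outcome (25% v 15%, 90% power, two-sided 0.05). With pooled variance and no continuity correction:

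n per arm = [1.960·√(2·0.20·0.80) + 1.282·√(0.25·0.75 + 0.15·0.85)]² / 0.10² = (1.109 + 0.719)² / 0.01 ≈ 334.2, rounded up to 335.

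The total is 670, as stated in SAP 3.3.

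**3. Inputs.**
- From protocol V3.0: 970 enrolled (1.4) and 10% loss to follow-up (5.4.4), giving 970 × 0.90 / 2 = 436.5 per arm.
- From the documents: equal allocation and two-sided 0.05.
- Assumed: true new-onset rates of 20% v 30%, and a share b of children with at least one carried-over counted symptom.

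**4. Any-occurrence count, as written.** A carried-over child is an event in either arm, so the observed rate is q = b + (1 − b)p. The difference is (1 − b)(p₁ − p₀).

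Power = Φ[(d − 1.96·se₀)/se₁], with se₀ = √(2q̄(1 − q̄)/n) and se₁ = √([q₀(1 − q₀) + q₁(1 − q₁)]/n).

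For b = 0.5 the rates are 60% v 65%, se₀ = 0.03277 and se₁ = 0.03273. Then (0.05 − 0.06423)/0.03273 = −0.435, and power is 33%.

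**5. New-onset count.** If carried-over children keep their full risk of a different new symptom, the rates stay at 20% v 30% for every b. If they keep none, the rates are (1 − b)p.

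| Carry-over b | As written: rates | Power | New-onset, full risk kept | New-onset, no risk kept: rates | Power |
|---|---|---|---|---|---|
| 0 | 20% v 30% | 93% | 93% | 20% v 30% | 93% |
| 10% | 28% v 37% | 81% | 93% | 18% v 27% | 89% |
| 20% | 36% v 44% | 68% | 93% | 16% v 24% | 84% |
| 50% | 60% v 65% | 33% | 93% | 10% v 15% | 61% |
| 70% | 76% v 79% | 18% | 93% | 6% v 9% | 39% |

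**6. Other assumed rates.** With 10% v 15%, power as written goes from 61% with no carry-over to 25% at b = 20% and 11% at b = 50%. With 30% v 40% it goes from 87% to 66% and 35%.

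The calculation ignores the stratification of the planned Mantel-Haenszel test.

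**The case against.** The strongest reply is that silence is not a rule. No text says that baseline symptoms are to be counted. SAP 5.6 leaves derived variables to dataset specifications, and neither these nor the case report forms are in the file. The survey may ask only about new symptoms. A reader might infer that the plan knowingly counts pre-existing symptoms as side effects. The documents do not support that: they support only that 7.4.1 states no new-onset condition.

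Second, the aggregate is not the only comparison. Protocol 5.1 (Specific Aim 2) also plans to tabulate and compare the listed side effects by arm. A carried-over loss of appetite hides nothing in the constipation row. This limits the harm. Each row can still be diluted, but only by that symptom's own baseline prevalence. The SAP does not repeat this comparison.

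Third, the symptoms judged most common are already removed from the initial window. SAP 7.4.2 says only that side effects are generally not adverse events, and protocol 8.3.3 still makes worsening reportable. Both are true, and neither gives the other 19 terms a new-onset condition.

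Fourth, the numbers are assumed. A reader could start at 90% carry-over and conclude that power falls from 93% to 8%. Nothing in the documents supports that share, and 93% is a best case for the new-onset count, because a child with baseline nausea cannot have new nausea. If carried-over children kept no remaining risk, the new-onset count at 90% carry-over would itself have only 16%. It still has more power than the any-occurrence count at every carry-over share above zero in the table.

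**Conclusion.** The point holds as a gap in SAP 7.4.1 that should be closed. As written, the any-symptom comparison has no new-onset condition for 19 of 23 terms, and the adverse-event rule that would have supplied one does not apply to them. Any carry-over shrinks the risk difference by the factor (1 − b), in the direction that favors the hypothesis of similar rates. The window through day 35 inherits this because it contains the first window.

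The direction follows from the text and simple algebra. The size does not: the carry-over share and the new-onset rates are assumptions, and the powers above are illustrations. A reader might also infer that the comparison is biased toward a false finding or that the test is invalid. It is not. Randomization balances carried-over symptoms, so type I error is unaffected and the loss is one of sensitivity. The primary efficacy analysis is not touched.

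**What to change.** Add a prespecified new-onset analysis to 7.4.1 for both windows, reported beside the any-occurrence comparison and with the same stratified test. Keep the present handling of diarrhea, vomiting, fever and diaper rash. Count any other listed symptom as new if it was recorded absent at randomization. Where baseline status was not recorded, count it if it is first reported on a survey that follows a survey without it. Count worsening only where severity of that symptom was collected. Carry the by-arm comparison of the listed side effects in protocol 5.1 into the SAP, symptom by symptom. Check the case report forms first: if the survey question is already limited to new symptoms, 7.4.1 should say so.

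The cost is SAP wording, one more derived variable and added table rows, using surveys already collected. There is a real downside. Protocol 8.3.1 describes side-effect collection at follow-up contacts, and the imputation plan in SAP 7.2.1 lists most of these symptoms only as post-randomization variables. Baseline status may therefore be missing for most terms, and the survey rule may become the main rule. It misses effects that start between the first dose and the first survey, so the any-occurrence result must stay alongside it. The SAP should state this limitation.

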## 2.1 Rationale for Probiotic Efficacy

Probiotics, defined as viable microbial preparations with beneficial effects on the health of the host, are regarded as safe, and are generally affordable and convenient (i.e., as over-the-counter food supplements). Probiotics, and *Lactobacillus rhamnosus* GG, ATCC

53103 (LGG) in particular, promote colonization resistance and modulate immune responses in the host, and can be directly antimicrobial. Over 100 studies have studied how probiotics can improve immune function in humans. At the mucosal surface, probiotics:

- compete with pathogenic bacteria for nutrients and adhesion binding sites;
- produce antimicrobial substances;
- provide nutrients to colonocytes;
- alter epithelial gene expression; and
- reduce intestinal permeability.

Additional mechanisms of action include enhancing phagocyte and natural killer cell activity, and increasing fecal, salivary, and systemic IgA levels.

Preliminary probiotic studies in humans, including over 56 trials in children with gastroenteritis (17 of which used some form of *Lactobacillus rhamnosus* GG, ATCC 53103 (LGG) , the agent employed in this trial) suggest that probiotics may improve the course of acute gastroenteritis. Meta-analyses report reduced mean duration of diarrhea (by 25 hours), reduced proportion of diarrhea lasting four days (risk ratio 0.41), and reduced stool frequency on Day 2 (mean difference 0.8). This has prompted some physicians and institutions to recommend probiotics in children with acute gastroenteritis. Careful examination of the data, however, shows significant methodological flaws in these studies. For these reasons, experts and agencies have continued to recommend large, unbiased, well designed definitive trials to inform practice.

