### 3.4 Follow Up Data Collection

Successful follow up will be maximized by obtaining multiple phone numbers for families and emergency contacts, scheduling calls and sending phone text reminders, allowing for electronic completion and centralizing all follow-up procedures at the lead institution (Washington University). Trained, experienced study staff will contact the family daily (including weekends) until both the diarrhea and vomiting have resolved and the treatment has been completed on day 5. Additional contact will be made on day 14 for outcome assessment, and months 1, 3, 6, 9 and 12 for long term safety outcomes. Study staff will use a standardized data collection form, and will inquire about ongoing symptoms, medical evaluations, treatments, child care, work absenteeism, and side effects. Detailed questioning will follow positive responses. A study diary will be provided to caregivers to use as a note-taking tool. Caregivers may also be provided an option of completing the follow-up collection electronically. Patient compliance with study drug administration will be assessed on day 5. To maximize compliance, caregivers will be reminded of the importance and method of administering the study drug. On day 14, the study site staff (not the central staff conducting the follow up) will perform a chart review for final data collection and identification of recorded adverse events during the 14 day study period. Adverse event reporting is described in detail in Section 8.3 on page 33.

Every effort will be made complete daily follow-up on the day necessary. However, if one or two days of follow-up contact is missed, data for those missed days may be collected on the next contact, if the caregiver used the home diaries or can recall the information. If all contact is missed but then the parent is contacted on day 14, follow-up data for the daily calls will be collected only if the parent diaries were used. For day 5 and 14, contact may be made within + 3 days. For month 1, 3, 6, 9, and 12 follow-up, contact may be made within  $\pm 2$  weeks.

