## Home Study Drug Administration

All patients will consume one capsule twice a day for 5 days (total of 9 home doses). Patients will receive the medication mixed with 20-30 mL of a room temperature non-carbonated liquid (or 1 tablespoon of applesauce as an alternative to liquid) and ingested immediately to optimize probiotic viability. One extra dose/day will be provided (i.e. kits will contain 5 extra doses total of 15 capsules) to account for vomiting or wastage. The dose may be repeated once if vomiting occurs within 15 minutes of administration; this rarely happens more than once. Oral fluid therapy will be encouraged according to established guidelines.

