## 7.2 Analysis of Primary Outcome

The primary outcome for the study is a post-enrollment (2-week) modified Vesikari Score (MVS), defined as  $MVS \geq 9$ . The scientific hypotheses regarding the primary outcome are described in Section 3.3.

The post-enrollment score is calculated based on the elements of the score collected Day 1 through Day 14, or when symptoms resolve. Resolution of symptoms is defined as the first

Points	0	1	2	3
Diarrhea duration	0	1–96 hrs	97–120 hrs	≥ 121 hrs
Max # of diarrheal stools/24 hrs	0	1–3	4–5	≥ 6
Vomiting duration	0	1–24 hrs	25–48 hrs	≥ 49 hrs
Max # of vomiting episodes/24 hrs	0	1	2–4	≥ 5
Max recorded fever	≤ 37°C	37.1–38.4°C	38.5–38.9°C	≥ 39°C
Unscheduled healthcare visit	0	—	Primary Care	Emergency Department
Treatment	None	Rehydration	Hospital Admission	—

Table 1: Modified Vesikari Score

daily survey with absence of both diarrhea and vomiting. Each of the seven components will be assigned a score for the entire study period (from randomization to day 14). Scoring of each component is described in Table 1.

The components will be calculated by the following rules:

- 1. Maximum number of episodes of vomiting in a 24-hour period.** The number of episodes of vomiting is not collected precisely in 24-hour blocks. However, this component will be defined as the maximum number of vomiting episodes reported on a single daily follow-up survey.
- 2. Maximum number of episodes of diarrhea in a 24-hour period.** This will use the same procedure as the previous component.
- 3. Maximum temperature.** This will also use the same procedure as the two above.

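### The first side-effect window in SAP 7.4.1 ends at each child's symptom resolution, so that one comparison would understate side effects on probiotic if the drug shortens illness

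*Combined protocol and SAP*

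**What the plan says.** SAP 7.4.1 (version 1.2) turns the listed side effects into a single yes/no outcome per child and tests it in two windows with a Mantel-Haenszel test stratified by center and symptom duration.

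- **First window:** "the initial disease window (through day 14, or until resolution of symptoms". Diarrhea, vomiting, fever and diaper rash are not counted in it.
- **Second window:** "through day 35 (which includes the initial window". For the four symptoms just named there is an exception: "The latter window will only count diarrhea, vomiting, fever, or diaper rash that occur after the initial disease window".

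SAP 7.4.1 does not define resolution. SAP 7.2 does so for the primary score, as the first "daily survey with absence of both diarrhea and vomiting". Neither window is named as the main one.

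Two protocol passages bear on this. On dosing, section 4.2 says: "All patients will consume one capsule twice a day for 5 days (total of 9 home doses". On data collection, section 3.4 says staff will "contact the family daily (including weekends) until both the diarrhea and vomiting have resolved and the treatment has been completed on day 5", with further contacts at day 14 and month 1.

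**The concern.** The length of the first window is itself an outcome. Diarrhea and vomiting durations are components of the primary score and are also secondary outcomes, so the trial is designed to detect a drug effect on the very quantity that closes the window. A child whose symptoms resolve on day 2 contributes nothing to this window on days 3 to 5. That child is still on study drug, and the family is still being contacted every day.

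A yes/no proportion grows with time at risk. If the probiotic shortens illness, its arm is observed for less time, and the comparison leans toward fewer side effects on probiotic even when the daily risk is identical.

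The second primary objective (SAP 2.1.1) includes a similar rate of side effects in the two arms, and this window is the only one of the two that looks closely at the early, on-treatment period. The fixed adverse-event period does not act as a backstop for these items, because SAP 7.4.2 generally does not count listed side effects as adverse events.

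**Working it through.** **Anchor.** The documents give no planning figure for the side-effect comparison. The nearest one is the 670 in SAP 3.3, used here only to fix the arm size. With 25% vs 15%, two-sided alpha 0.05 and 90% power, n per arm = [1.96·√(2·0.20·0.80) + 1.282·√(0.25·0.75 + 0.15·0.85)]² / 0.10² ≈ 334.2, rounded up to 335, so the total is 670 as stated. The SAP target of 900 less 10% loss is 810, or 405 per arm.

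**Inputs.**
- Shortening of illness: 25 hours (25/24 = 1.04 days). Protocol 2.1 says meta-analyses "report reduced mean duration of diarrhea (by 25 hours". A 12-hour effect and no effect are also shown.
- Mean time from randomization to resolution on placebo: not in the documents. Assumed 3 or 5 days.
- Daily hazard of a first countable side effect: not in the documents. Assumed constant, equal in both arms, 3% to 20%.

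**Step 1, simple check.** Risk in the window = 1 − exp(−h·d), where d is the window length in days. With d = 3.00 on placebo, d on probiotic is 3.00 − 1.04 = 1.96. With d = 5.00 it is 3.96.

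| Daily hazard | 3-day window: placebo vs probiotic | Difference | 5-day window: placebo vs probiotic | Difference |
|---|---|---|---|---|
| 3% | 8.6% vs 5.7% | 2.9 points | 13.9% vs 11.2% | 2.7 points |
| 5% | 13.9% vs 9.3% | 4.6 points | 22.1% vs 18.0% | 4.2 points |
| 10% | 25.9% vs 17.8% | 8.1 points | 39.3% vs 32.7% | 6.7 points |
| 20% | 45.1% vs 32.4% | 12.7 points | 63.2% vs 54.7% | 8.5 points |

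All of these differences arise with no true difference in daily risk.

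**Step 2, letting duration vary between children.** Time to resolution is taken as gamma with shape 2 and placebo mean 2.5 to 5 days, the window as the smaller of 14 days and resolution, and the placebo proportion with a side effect as 20% to 60%, with 405 per arm and no stratification.

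| Shorter illness on probiotic | Apparent difference | Chance of a significant result favoring probiotic | True rate ratio that would appear as no difference |
|---|---|---|---|
| 25 hours | −3.5 to −15.8 points | 26% to 99% | 1.25 to 1.71 |
| 12 hours | −1.7 to −6.6 points | 9% to 47% | 1.11 to 1.25 |
| None | 0 | 2.5% (nominal) | 1.00 |

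In these scenarios 59% to 91% of placebo children resolve before day 5, so for most children part of the dosing period falls outside the first window.

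**Step 3, the day-35 window.** SAP 2.2.2 lists 23 side effects. Four have a start that depends on resolution; the other 19 run from randomization to day 35 for every child. For the four, a 3-day placebo mean gives 35 − 3.00 = 32.00 days at risk on placebo and 33.04 on probiotic, about 3% more. At placebo rates of 10% to 50% that adds 0.3 to 1.1 points on probiotic: small, and against the drug.

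**The case against.** A reader might infer that both windows are unsound, biased in opposite directions, and that the side-effect comparison as a whole is compromised. The documents do not support that. The day-35 window contains the first one and has the same end for every child. A child who recovers on day 2 and has bloating on day 4 is counted there. Only four of 23 items start at a child-specific time, and the effect of that is minor. The primary safety endpoint of invasive disease, adverse events to 35 days, and serious adverse events to one year after the last dose are not tied to resolution.

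The size can also be challenged. The placebo window length and the hazards are assumed. The 25 hours refers to diarrhea alone and comes from trials that protocol 2.1 itself calls flawed, whereas the window closes only when vomiting is absent too. Several listed items, such as nausea, cramps and loss of appetite, overlap with the illness. They would cluster early, which shrinks the artifact, and fewer of them after a shorter illness may be real benefit.

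All of this stands, and it narrows the point to one of two planned comparisons. It does not remove it. The day-35 comparison mixes about 5 days of dosing with about 30 days of background symptoms, so it is a blunt check on early tolerability. With no main window named, the resolution-based result could be reported as the early safety finding.

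**Conclusion.** The point holds for the first window of SAP 7.4.1 only. If the probiotic shortens illness by 25 hours and the daily hazard is constant and equal in both arms at 3% to 20%, that comparison understates side effects on probiotic by roughly 3 to 13 points with a 3-day placebo window, or 3 to 9 points with a 5-day window. A smaller effect on duration gives a smaller distortion, and no effect gives none. The direction is certain if illness is shortened and daily risk is otherwise equal; the size depends on inputs that the documents do not supply. The day-35 comparison is not materially affected. The change is worth making because the problem would appear exactly when the trial succeeds, and avoiding it costs almost nothing.

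**What to change.** In SAP 7.4.1:

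1. For the side effects counted in the first window, replace the resolution-based end with randomization through day 5 for every child. All families are due daily contact over that period, so capture is planned to be the same in both arms.
2. Add randomization through day 14, regardless of resolution, as a supporting analysis. State that after day 5 daily contact continues only for children who are still ill, so capture between day 5 and the day-14 contact is less even.
3. Name the through-day-35 comparison as the main overall one.
4. Keep the present rule that counts diarrhea, vomiting, fever and diaper rash after resolution in the day-35 window. Starting those four at day 15 for everyone looks tidier, but it would lose recurrences between resolution and day 14. Those recurrences are outside the primary score, because protocol 5.1 treats a relapse after both symptoms stop as a new illness, and they are generally not recorded as adverse events.

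The cost is a wording change and one extra table, with no new data collection. The downside is that a 5-day window misses later events; the day-14 and day-35 comparisons cover those.
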